5.3. Lifestyle Considerations

Not applicable, no restrictions are required.

5.3.1. Contraception

The investigator or his or her designee, in consultation with the participant, will confirm that the participant has selected an appropriate method of contraception for the individual participant and his or her partner(s) from the permitted list of contraception methods (see [Appendix 4](#)) and will confirm that the participant has been instructed in its consistent and correct use. At time points indicated in the schedule of activities ([SoA](#)), the investigator or designee will inform the participant of the need to use highly effective contraception consistently and correctly and document the conversation and the participant's affirmation in the participant's chart (participants need to affirm their consistent and correct use of at least 1 of the selected methods of contraception). In addition, the investigator or designee will instruct the participant to call immediately if the selected contraception method is discontinued or if pregnancy is known or suspected in the participant or partner.

5.4. Screen Failures

Screen failures are defined as participants who consent to participate in the clinical study but are not subsequently enrolled in the study. A minimal set of screen failure information is required to ensure transparent reporting of screen failure participants to meet the CONSORT publishing requirements and to respond to queries from regulatory authorities. Minimal information includes demography, screen failure details, eligibility criteria, and any SAE.

Individuals who do not meet the criteria for participation in this study (screen failure) may be rescreened twice after the initial screen fail.

6. STUDY INTERVENTION

Study intervention is defined as any investigational intervention(s), marketed product(s), placebo, medical device(s), or study procedure(s) intended to be administered to a study participant according to the study protocol.

For the purposes of this protocol, study intervention refers to PF-07209960.

6.1. Study Intervention(s) Administered

Intervention Name	PF-07209960
ARM Name (group of participants receiving a specific treatment (or no treatment))	All
Type	Biologic
Dose Formulation	Lyophilized powder for solution for injection or infusion
Unit Dose Strength(s)	10 mg/vial
Dosage Level(s)	Dose amount and frequency – reference the study scheme/figure or text below as appropriate.
Route of Administration	SC (or IV if necessary)
Use	Experimental
IMP or NIMP	IMP
Sourcing	Provided centrally by the sponsor. Specifics on ordering can be found in the IP manual.
Packaging and Labeling	Study intervention will be provided in single vials packaged in individual cartons. Each vial and carton will be labeled as required per country requirement. IP will be provided as open labeled material.
Current Name	PF-07209960, Targeted IL-15

PF-07209960 10 mg/vial is presented as a sterile lyophilized powder for solution for SC or IV administration. Each vial contains 10 mg of PF-07209960 as a white cake essentially free from visible particulates in a 6 mL type I clear glass vial, sealed with a 13 mm lyo stopper and 13 mm aluminum flip-off seal.

6.1.1. Administration

PF-07209960 will be administered once every 2 weeks as a flat dose SC injection or IV infusion over 1 hour (± 10 minutes).

Each participant may receive PF-07209960 until disease progression, unacceptable toxicity, withdrawal of consent, or study termination. Treatment beyond disease progression may be discussed with sponsor if the investigator assesses that it is the participant's best interest to continue with treatment and would not derive as much benefit from alternative therapy and has met the criteria for treatment beyond progression as outlined in [Section 4](#) .

Subcutaneous administration

Qualified and trained investigator site personnel will administer PF-07209960 to participants by SC injection. Ideally, each injection may be up to 2 mLs in volume. However, if the maximum volume allowed per institution's policy is lower, the number of injections may

increase to accommodate this difference in volume to ensure the correct final dose is delivered.

Study drug should be administered to the abdomen (with preference given to the lower quadrants when possible). Refer to [Appendix 12](#), for details on administration of multiple injections to the abdomen. Study staff should refer to the IP Manual for specific instructions on the handling and preparation of study drug.

Cycle duration: A cycle is defined as 28 days, regardless of missed doses or dose delays.

Intravenous administration

Based on the available emerging clinical data (including safety/tolerability, PK, PD) from the dose escalation cohorts with SC Q2W administration, IV infusion Q2W administration may be explored in successive dose cohorts. If IV administration is introduced, PF-07209960 will be administered over 1 hour (± 10 minutes) time period without adjustment for body size at every cycle as indicated in the IP manual.

6.2. Preparation/Handling/Storage/Accountability

1. The investigator or designee must confirm appropriate temperature conditions have been maintained during transit for all study interventions received and any discrepancies are reported and resolved before use of the study intervention.
2. Only participants enrolled in the study may receive study intervention and only authorized site staff may supply or administer study intervention. All study interventions must be stored in a secure, environmentally controlled, and monitored (manual or automated recording) area in accordance with the labeled storage conditions with access limited to the investigator and authorized site staff. At a minimum, daily minimum and maximum temperatures for all site storage locations must be documented and available upon request. Data for nonworking days must indicate the minimum and maximum temperatures since previously documented for all site storage locations upon return to business.
3. Any excursions from the study intervention label storage conditions should be reported to Pfizer upon discovery along with any actions taken. The site should actively pursue options for returning the study intervention to the storage conditions described in the labeling, as soon as possible. Once an excursion is identified, the study intervention must be quarantined and not used until Pfizer provides permission to use the study intervention. Specific details regarding the definition of an excursion and information the site should report for each excursion will be provided to the site in the IP manual.
4. Any storage conditions stated in the SRSD will be superseded by the storage conditions stated on the label.
5. Study interventions should be stored in their original containers.
6. See the IP manual for storage conditions of the study intervention once reconstituted.

7. The investigator, institution, or the head of the medical institution (where applicable) is responsible for study intervention accountability, reconciliation, and record maintenance (ie, receipt, reconciliation, and final disposition records), such as the IPAL or sponsor-approved equivalent. All study interventions will be accounted for using a study intervention accountability form/record.
8. Further guidance and information for the final disposition of unused study interventions are provided in the IP manual. All destruction must be adequately documented. If destruction is authorized to take place at the investigator site, the investigator must ensure that the materials are destroyed in compliance with applicable environmental regulations, institutional policy, and any special instructions provided by Pfizer.

Upon identification of a product complaint, notify the sponsor within 1 business day of discovery as described in the IP Manual.

6.2.1. Preparation and Dispensing

See the IP manual for instructions on how to prepare the study intervention for administration. Study intervention should be prepared and dispensed by an appropriately qualified and experienced member of the study staff (eg, physician, nurse, physician's assistant, nurse practitioner, pharmacy assistant/technician, or pharmacist) as allowed by local, state, and institutional guidance. A second staff member will verify the dispensing. Vials are single-use.

Only qualified personnel who are familiar with procedures that minimize undue exposure to themselves and to the environment should undertake the preparation, handling, and safe disposal of biologic agents.

6.3. Measures to Minimize Bias: Randomization and Blinding

6.3.1. Allocation to Study Intervention

Part 1: Dose Escalation

Dose level allocation will be performed by the sponsor after participants have given their written informed consent and have completed the necessary baseline assessments. The site staff will fax/e-mail a complete Registration Form to the designated sponsor study team member or designee. The sponsor will assign a participant identification number and supply this number to the site. The participant identification number will be used on all study-related documentation at the site.

No participant will receive study intervention until the investigator or designee has received the following information in writing from the sponsor:

- Confirmation of the participant's enrolment;
- Specification of the dose level for that participant and;
- Permission to proceed with dosing the participant.

Study intervention will be dispensed at the study visits summarized in the [SoA](#).

Returned study intervention must not be redispensed to the participant.

Part 2: Dose Expansion

If IRT will be utilized for Dose Expansion, allocation of participants to treatment groups will proceed through the use of an IRT system (IWR). If IRT will not be used, the Dose Expansion will follow the dose level allocation as indicated in the above Part 1, Dose Escalation section. The site personnel (study coordinator or specified designee) will be required to have an active or valid account and password with the IRT system, enter or select information including but not limited to the users' ID and password, protocol number, specific protocol entrance criteria indicated in the system and the participant number. The site personnel will then be provided with, at a minimum, a treatment assignment, randomization number, and DU or container number when study intervention is being supplied via the IRT system. The IRT system will provide a confirmation report containing the participant number, randomization number, and DU or container number assigned. The confirmation report must be stored in the site's files.

Study intervention will be dispensed at the study visits as summarized in the [SoA](#).

Returned study intervention must not be redispensed to the participants.

The study-specific IRT reference manual will provide the contact information and further details on the use of the IRT system.

6.4. Study Intervention Compliance

When participants are dosed at the site, they will receive study intervention directly from the investigator or designee, under medical supervision. The date and time of each dose administered in the clinic will be recorded in the source documents and recorded in the CRF. The dose of study intervention and study participant identification will be confirmed at the time of dosing by a member of the study site staff other than the person administering the study intervention.

The site will complete the required dosage Preparation Record located in the IP manual. The use of the Preparation Record is preferred, but it does not preclude the use of an existing appropriate clinical site documentation system. The existing clinical site's documentation system should capture all pertinent/required information on the preparation and administration of the dose. This may be used in place of the Preparation Record after approval from the sponsor and/or designee.

6.5. Concomitant Therapy

Concomitant treatment considered necessary for the participant's well-being may be given at discretion of the treating physician.

All concomitant treatments, blood products, as well as nondrug interventions received by participants from screening until the end of treatment visit will be recorded on the CRF.

PF-07209960 has been demonstrated to transiently increase cytokine levels (eg, IL-6) in vivo in monkeys (also demonstrated via in vitro assays). Cytokines have been shown to result in modulation of the expression of some cytochrome P450 enzymes. Therefore, treatment with PF-07209960 may potentially result in modest increase in the exposure of concomitant medications that are substrates for these enzymes. Caution should be used upon concomitant use of sensitive substrates of cytochrome P450 enzymes with narrow therapeutic index (eg, CYP3A4: alfentanil, cyclosporine, dihydroergotamine, ergotamine, fentanyl, pimozide, quinidine, sirolimus and tacrolimus; CYP2C9: phenytoin, warfarin) especially during the initial treatment cycle.

6.5.1. Other Anti-tumor/Anti-cancer or Experimental Drugs

No additional anti-tumor treatment will be permitted while participants are receiving study treatment. Additionally, the concurrent use of vitamins beyond a daily multivitamin or supplementation for a documented vitamin deficiency or herbal supplements is not permitted.

6.5.2. Radiation Therapy

Palliative radiotherapy to a limited field but not to a target lesion(s) is allowed after consultation with sponsor's Medical Monitor at any time during study participation, including during screening, unless clearly indicative of disease progression. In view of the current lack of data about the interaction of PF-07209960 with radiotherapy, PF-07209960 treatment should be interrupted during palliative radiotherapy, stopping 7 days before and resuming treatment after 7 days. If the effects of palliative radiotherapy on overall anti-tumor efficacy cannot be clearly distinguished from those of PF-07209960 following radiotherapy, response assessments after radiotherapy should be considered as non-evaluable.

6.5.3. Supportive Care

Palliative and supportive care for disease related symptoms may be administered at the investigator's discretion and according to the specific supportive care product Prescribing Information or the current ASCO guidelines ([ASCO, 2020](#)).

6.5.4. Hematopoietic Growth Factors

During the 14 days prior to Day 1, granulocyte colony stimulating factors are not permitted to qualify a participant with low WBC counts.

Primary prophylactic use of colony stimulating factors is not permitted during the first 28 days of Cycle 1 Part 1, but they may be used to treat treatment emergent neutropenia as indicated by the current ASCO guidelines ([ASCO, 2020](#)).

Erythropoietin may be used at the investigator's discretion for the supportive treatment of anemia.

6.5.5. Anticoagulation Therapy

Anticoagulation therapy with vitamin K antagonists is prohibited throughout the study and for at least 28 days post the last dose of study treatment. Anticoagulation with low molecular weight heparin and Factor Xa inhibitors or use of antiplatelet therapy is allowed but must be held per institutional requirements for biopsies and whenever platelet count is $<50,000/\text{mm}^3$ or when active bleeding occurs and resume only when platelet count is $>50,000/\text{mm}^3$ and there is no bleeding.

Antiplatelet therapy must be held during the first week of PF-07209960 and may resume if it is observed that the platelet count does not drop below $50,000/\text{mm}^3$ the first week after receiving PF-07209960, and the platelet count has reached a nadir and shown a subsequent increase. If platelet count does drop below $50,000/\text{mm}^3$ the first week after receiving PF-07209960, then antiplatelet agents should be held during the first week following every administration of PF-07209960. All antiplatelet therapy should be held per institutional requirements for biopsies and stopped when platelet count is $<50,000/\text{mm}^3$ or when active bleeding occurs and resume only when platelet count is $>50,000/\text{mm}^3$ and there is no bleeding. Platelet transfusions should be considered for active bleeding and platelet count $<50,000/\text{mm}^3$.

6.5.6. Anti-Diarrheal, Anti-Emetic Therapy

Primary prophylaxis beyond the first dose is at the investigator's discretion. The choice of the prophylactic drug as well as the duration of treatment is up to the investigator assuming there is no known or expected drug-drug interaction and assuming the drug is not listed in the [Concomitant Therapy](#) section. If irAE of diarrhea or colitis is suspected, please refer to [Appendix 14](#) for guidance on the management of irAEs.

6.5.7. Anti-Inflammatory Therapy

Anti-inflammatory or narcotic analgesic may be offered as needed assuming there is no known or expected drug-drug interaction and assuming the drug is not included in the [Concomitant Therapy](#) section.

6.5.8. Corticosteroids

Chronic systemic corticosteroid use (prednisone $>10 \text{ mg/day}$ or equivalents) for palliative or supportive purposes is not permitted. Acute emergency administration (eg, for prophylaxis and/or management of CRS or other toxicities), topical applications, inhaled sprays, eye drops, or local injections of corticosteroids are allowed.

6.5.9. Surgery

Caution is advised on theoretical grounds for any surgical procedures during the study. The appropriate interval of time between surgery and PF-07209960 required to minimize the risk of impaired wound healing and bleeding has not been determined. Stopping PF-07209960 is recommended at least 7 days prior to surgery. Post-operatively, the decision to reinitiate PF-07209960 treatment should be based on a clinical assessment of satisfactory wound healing and recovery from surgery.

6.5.10. Transfusion Support

Primary prophylactic use of transfusion support for anemia is allowed to treat anemia, as indicated by the current American Society of Clinical Oncology and American Association of Blood Banks guidelines ([Carson et al, 2016](#)). Primary prophylactic use of transfusion support for thrombocytopenia is allowed during screening if the transfusion is completed prior to planned study treatment start. Primary prophylactic use of transfusion support for thrombocytopenia is allowed to treat thrombocytopenia, as indicated by the current American Society of Clinical Oncology ([Schiffer et al, 2018](#)).

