5. STUDY POPULATION

This study can fulfill its objectives only if appropriate participants are enrolled. The following eligibility criteria are designed to select participants for whom participation in the study is considered appropriate. All relevant medical and nonmedical conditions should be taken into consideration when deciding whether a particular participant is suitable for this protocol.

Prospective approval of protocol deviations to recruitment and enrollment criteria, also known as protocol waivers or exemptions, is not permitted.

Pfizer will review eligibility criteria verified by the investigator or qualified designee to confirm that participants meet study eligibility criteria before they are enrolled into the study. The enrollment approval process will be initiated for a participant after an informed consent document has been signed and the investigator or qualified designee has assessed the participant as eligible. The enrollment approval will be based on review of CRF/system data.

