of platinum-containing chemotherapy followed by anti-PD-1/PD-L1 maintenance therapy.

- d) Participants with MSS CRC must have received ≥ 2 prior lines of therapy including treatment regimens containing combinations of pyrimidine analog, oxaliplatin, irinotecan, anti-EGFR (RAS wild type), encorafenib (if BRAF V600E-positive) and anti-HER2 (if HER2-amplified and RAS and BRAF wild type).
- e) Participants with OvCa must have received ≥ 2 prior lines of therapy including at least 1 regimen with platinum-based chemotherapy and progressed on last two consecutive regimens without evidence of clinical benefit.

3. Participants entering the study in ≥ 1 measurable lesion (at least 10 mm in the longest diameter by CT scan/MRI for non-lymph nodes and at least 15 mm in the short axis for lymph nodes) as defined by RECIST version 1.1 that has not been previously irradiated.
4. Must have tumor tissue available for submission to the sponsor:
 - a. Participants enrolled in Part 1 and Part 2 should consent to undergo biopsy during screening (pre-treatment) or be able to provide archival FFPE material containing tumor that is of diagnostic quality and representative of their diagnosed malignancy taken ≤ 1 year prior to study start. If the archival sample is older than 1 year and a biopsy during screening cannot be performed, the investigator must contact the sponsor to discuss eligibility prior to enrollment.
 - b. Participants enrolled in Part 2 dose expansion must have a tumor amenable to biopsy and consent to planned mandatory pre- and on-treatment biopsy procedures until the sponsor deems that an adequate number of participants (10-15 paired fresh biopsies per cohort) have been successfully biopsied, at which point participants will only be required to submit pre-treatment biopsies (either archival tissue or de novo biopsy as above). Special considerations will be made for participants with poorly accessible tumors or deemed medically unsafe as determined by the investigator after discussion and agreement by the sponsor.
5. ECOG PS 0-2 for Part 1, 0-1 for Part 2.
6. Adequate hematologic function, including:
 - a. ANC $\geq 1,500/\text{mm}^3$ or $\geq 1.5 \times 10^9/\text{L}$;
 - b. Platelets $\geq 100,000/\text{mm}^3$ or $\geq 100 \times 10^9/\text{L}$;

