 - c. Hemoglobin $\geq 9 \text{ g/dL}$. Limited transfusions to reach this value are allowed, after discussion with the sponsor's medical monitor. There should not be chronic need for transfusions (>1 per month) in the recent (approximately 3 months) past.
7. Adequate renal function, including:
 - d. Estimated creatinine clearance $\geq 50 \text{ mL/min}$ as calculated by Cockcroft-Gault method. In equivocal cases, a 24-hour urine collection test can be used to estimate the creatinine clearance more accurately.

8. Adequate liver function, including:
 - a. Total serum bilirubin $\leq 1.5 \times$ ULN;
 - b. AST and ALT $\leq 2.5 \times$ ULN; $\leq 5.0 \times$ ULN if there is liver involvement by the tumor;
 - c. Alkaline phosphatase $\leq 2.5 \times$ ULN ($\leq 5 \times$ ULN in case of bone metastasis).
9. Adequate coagulation function, including:
 - a. INR or aPTT $\leq 1.5 \times$ ULN.
10. LVEF $\geq 50\%$ by echocardiogram or MUGA.
11. Resolved acute effects of any prior therapy to baseline severity or CTCAE Grade ≤ 1 except for AEs not constituting a safety risk by investigator judgment.
12. Willing and able to comply with all scheduled visits, treatment plan, laboratory tests, lifestyle considerations, and other study procedures.
13. Capable of giving signed informed consent as described in [Appendix 1](#), which includes compliance with the requirements and restrictions listed in the ICD and in this protocol.

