10. Abnormal cardiac valve morphology (\geq grade 2) documented by echocardiogram (participants with grade 1 abnormalities [ie, mild regurgitation/stenosis] can be enrolled on study). Participants with valvular thickening should not be enrolled into the study.
11. Anticoagulation with vitamin K antagonists is not allowed. Anticoagulation with low molecular weight heparin and Factor Xa inhibitors or use of antiplatelet therapy is allowed but must be held per institutional requirements for biopsies and whenever platelet count is $<50,000/\text{mm}^3$. If participants are on antiplatelet therapy, they must be able to hold antiplatelet therapy for first week of study treatment without significantly increased risk of cardiovascular events.
12. AEs from prior therapy which have not recovered to Grade ≤ 1 or baseline.
13. Hypertension Grade 3 or higher (eg, $\geq 160/100 \text{ mmHg}$) that cannot be controlled by medications despite optimal medical therapy.
14. Participation in other studies involving investigational drug(s) within 4 weeks prior to first dose.
15. Known or suspected hypersensitivity to any PF-07209960 components, or to mAbs or other therapeutic proteins such as fresh frozen plasma, human serum albumin, cytokines, or interleukins.
16. History of clinically significant Grade ≥ 3 immune mediated AE that was considered related to prior immune modulatory therapy (eg, immune checkpoint inhibitors, co stimulatory agents, etc.) and required immunosuppressive therapy. Patients with immune-mediated endocrinopathies controlled with hormonal replacement therapy (eg, thyroid disorders, diabetes, adrenal insufficiency) are eligible.
17. Active autoimmune disease that might deteriorate when receiving an immunostimulatory agent. Patients with diabetes type I, vitiligo, psoriasis, or hypo- or hyperthyroid disease not requiring immunosuppressive treatment are eligible.
18. Organ transplant requiring immunosuppressive treatment or prior allogeneic bone marrow or hematopoietic stem cell transplant.
19. Current use of immunosuppressive medication at the time of randomization, EXCEPT for the following: a) intranasal, inhaled, topical steroids, or local steroid injection (eg, intra-articular injection); b) Systemic corticosteroids at physiologic doses $\leq 10 \text{ mg/day}$ of prednisone or equivalent; c) Steroids as premedication for hypersensitivity reactions (eg, CT scan premedication).

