20. Active bleeding disorder, including gastrointestinal bleeding, as evidenced by hematemesis, significant hemoptysis or melena in the past 6 months prior to first dose.
21. History of interstitial lung disease or pneumonitis.

22. Participants with the presence of any open, active wound.
23. Pregnancy or breastfeeding.
24. Other medical or psychiatric condition including recent (within the past year) or active suicidal ideation/behavior or laboratory abnormality that may increase the risk of study participation or, in the investigator's judgment, make the participant inappropriate for the study.
25. Investigator site staff or Pfizer employees directly involved in the conduct of the study, site staff otherwise supervised by the investigator, and their respective family members.

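### No explicit text bars meeting the 100,000/mm³ platelet criterion on a transfused count: Section 6.5.10 sets no interval after a screening transfusion, and inclusion 6b does not ask for an untransfused value

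*Protocol*

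**What the plan says.** Protocol Section 5.1, inclusion 6 ("Adequate hematologic function, including") sets three thresholds. For platelets (6b) it gives only the value, at least 100,000/mm³. For hemoglobin (6c) it adds conditions on support: "Limited transfusions to reach this value are allowed, after discussion with the sponsor's medical monitor", and "There should not be chronic need for transfusions", with chronic need meaning more than one a month over roughly the last three months.

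Section 6.5.4 bars G-CSF in the 14 days before Day 1 as a way of qualifying someone with a low white cell count.

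Section 6.5.10 covers platelets: "Primary prophylactic use of transfusion support for thrombocytopenia is allowed during screening if the transfusion is completed prior to planned study treatment start". The next sentence allows prophylactic platelet transfusion in line with an oncology society guideline. Neither sentence sets an interval between a transfusion and the qualifying count.

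Section 2.3.1 counts platelet eligibility among its mitigations for thrombocytopenia with bleeding. The others are hematology and coagulation testing throughout, holding anticoagulants at low counts, and holding antiplatelet drugs for at least the first week.

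**The concern.** A transfused count shows donor platelets as well as the participant's own. If it can satisfy 6b, the criterion no longer ensures the platelet reserve that Section 2.3.1 relies on.

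This matters for this agent. Section 2.3 lists thrombocytopenia among the nonclinical findings with PF-07209960, and Section 2.2 reports it among the toxicities that stopped escalation of recombinant IL-15. What is at stake is the safety of an occasional participant in a first-in-human trial. Supported counts are regulated for the other two blood lines, so the silence on platelets looks like an omission and not a considered choice.

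**Working it through.** The point rests on the text. The plan has no figure of its own to reproduce.

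**Step 1. The three blood lines side by side**

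| Count | Threshold | Rule on support used to reach it |
|---|---|---|
| Neutrophils (6a) | ≥1,500/mm³ | No G-CSF to qualify in the 14 days before Day 1 (6.5.4) |
| Platelets (6b) | ≥100,000/mm³ | None; screening transfusion allowed if finished before first dose (6.5.10) |
| Hemoglobin (6c) | ≥9 g/dL | Limited, after medical monitor discussion, no chronic need (6c) |

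Only the platelet row has a permission to transfuse and no condition on the qualifying value.

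**Step 2. Do other rules close the gap?**

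- *Exclusion 12* covers "AEs from prior therapy which have not recovered to Grade" 1 or lower, or to baseline. Section 4.3.3 equates Grade 3 thrombocytopenia with a count below 50,000/mm³, so native counts below that from prior therapy are excluded unless they are at baseline. Other causes are not covered. The documents give no Grade 1/Grade 2 platelet cut, so the reach of exclusion 12 between 50,000 and 100,000 cannot be computed from them.
- *Inclusion 11* has the same scope and adds an exception: "except for AEs not constituting a safety risk by investigator judgment".
- *Exclusion 20* removes participants with an active bleeding disorder, shown by hematemesis, significant hemoptysis or melena, in the 6 months before first dose. It does not reach someone transfused preventively without such bleeding.
- *Exclusion 24* covers a "laboratory abnormality that may increase the risk of study participation". A known low native count could fit, but no platelet value or transfusion rule is stated.
- *Sponsor review* (Section 5) exists "to confirm that participants meet study eligibility criteria before they are enrolled into the study" and uses case report form data, on which blood products are recorded from screening (Section 6.5). In Part 1 the sponsor must also give written permission to dose (Section 6.3.1). The sponsor may well see the transfusion, but on the wording 6b would be met.
- *Monitoring.* Cycle 1 hematology is scheduled on Days 1, 2, 3, 4, 8, 15 and 22, and escalation participants stay in hospital for at least 72 hours. This would help detect a fading count, but no platelet minimum is tied to the first dose. The 50,000/mm³ rule in Section 6.6.2 applies to re-treatment after an interruption.

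Each rule narrows the exposure. None is an explicit bar.

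**Step 3. Illustration of reserve**

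The native counts N below 100 (thousands/mm³) are assumptions. Once transfused platelets have gone, the proportional fall that takes a count to 50 (Grade 3) is 1 − 50/N, and to 25 (Grade 4) it is 1 − 25/N.

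| N | Fall to 50 | Fall to 25 |
|---|---|---|
| 100 (untransfused, at 6b) | 50.0% | 75.0% |
| 90 | 44.4% | 72.2% |
| 80 | 37.5% | 68.8% |
| 70 | 28.6% | 64.3% |
| 60 | 16.7% | 58.3% |

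The table shows how the margin shrinks with the native count. It says nothing about how often this would occur, and it applies equally to an untransfused count that drifts down after screening.

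**The case against.** The strongest reply is that the scenario is close to empty. Section 6.5.10 allows prophylaxis for thrombocytopenia and does not mention transfusing to reach a value. Inclusion 6c uses that language for hemoglobin, and Section 6.5.4 speaks of qualifying for white cells, so silence in 6b can be read as no permission. The nearest stated trigger for platelet transfusion is active bleeding with a count below 50,000/mm³ (Section 6.5.5). Many such participants would fall under exclusion 20, and exclusion 12 removes low counts from prior therapy that are above Grade 1 and not at baseline. Nothing in the documents supports prophylactic transfusion at 60,000 to 90,000/mm³. The sponsor would have the transfusion record at review, and Cycle 1 monitoring is close.

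Much of this stands, and it keeps the point small. It does not remove it. Barring by contrast with 6c is an inference that sites may or may not draw, while the permission in 6.5.10 is explicit. The guideline that 6.5.10 cites might set a trigger, but the protocol takes no washout from it.

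A reader might also infer that transfused entry counts would distort DLT classification and hence the MTD. Section 4.3.3 requires a DLT to be a clinically significant shift from baseline, and SAP Section 3.4 takes the last value before first dose as baseline without setting post-transfusion values aside. The documents do not support the inference: they give no frequency, no native counts and no basis for the direction or size of an effect. Nor do they show that the sponsor means to let participants qualify by transfusion. The text is silent on that.

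**Conclusion.** The point holds as a gap in wording: no explicit text bars meeting 6b on a transfused count, although Section 2.3.1 relies on that criterion and the other two blood lines have a rule. It is more than missing detail, because a stated permission undercuts a stated safety threshold in a first-in-human trial.

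Its size is limited. The frequency cannot be estimated and is probably low, and existing exclusions, sponsor review and monitoring cover part of it. The percentages above rest on assumed native counts and are illustrative only. No effect on the MTD or any endpoint is shown. The change is a worthwhile, inexpensive improvement and does not put the design in doubt.

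**What to change.** Amend inclusion 6b to: *platelets ≥100,000/mm³ without platelet transfusion within 14 days before the qualifying sample*. Fourteen days borrows the length of the G-CSF rule in Section 6.5.4. The documents give no platelet figure, so the sponsor may set another window, for example 7 days. Add to Section 6.5.10: *platelet transfusion during screening may not be used to meet inclusion 6b*.

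A Day 1 platelet minimum for every participant, or a lockout of the first dose after any screening transfusion, would go further than the gap requires and is not proposed.

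The cost is two short text changes and no new data, because blood products are already recorded from screening. A few participants who need a platelet transfusion in screening will be delayed or become ineligible. With a 28-day screening window, a 14-day interval leaves 28 − 14 = 14 days, so a participant transfused early in screening can still qualify in the same period. Others can use the two rescreens in Section 5.4. If the sponsor does intend to accept transfused counts, it should say so in 6b and restate the mitigation in Section 2.3.1.
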